11.3 Timing

- The index procedure date is defined as Day 0. For randomized patients who do not have the procedure attempted, the randomization date will be used as Day 0.
- Time intervals for events will be computed by subtracting the event date minus day 0. For example, if the procedure occurs on January 1, and the patient dies on January 31, the death will be considered a 30 day death for analysis.
- The timing for all visits will be based on the index procedure date. If the patient never receives the procedure the 30-day visit will never be due; later visits for such patients will be based on the randomization date.
- In analysis of time-dependent variables, one year is defined as 365.25 days, and one month as 30.4375 (= 365.25/12) days.

For information depending on follow-up windows any visit within the specified window will be used, without regard to the actual timing of the visit.

- Analysis close date:
 - The analysis close date for the initial analysis will be the earlier of the following two dates: One year past the last index procedure
 - One year plus 60 days past the last randomization. This condition is in order to account for a potential patient with a severely delayed procedure.
- The analysis close date for later reports will be determined prior to the report. Unless otherwise specified such dates will be at annual intervals past the initial analysis close date.
- All database information will be used to determine patient survival as of the analysis close date.
- Adverse events occurring after the relevant analysis close date will not be included in adverse event analysis.
- Information dependent on a visit window, such as echo or NYHA, will be included in analysis as long as the window starts on or before the analysis close date.

11.4 Primary endpoint analysis (Non-inferiority)

The primary safety and effectiveness endpoint is the composite of all-cause mortality, all stroke, and rehospitalization (valve-related or procedure-related and including heart failure) at 1 year post procedure. The endpoint will be evaluated as a non-inferiority analysis based on a non-inferiority margin of 6.0%. The components of

the composite endpoint will be evaluated by the CEC.

To precisely formulate the test, let r_T denote the true event proportion in the test arm at 1 year, and r_C denote the true event proportion in the Control arm at 1 year. The hypotheses are:

$$\begin{aligned} H_0: r_T - r_C &\geq \Delta \\ H_A: r_T - r_C &< \Delta \end{aligned}$$

The value Δ is the non-inferiority margin, and is taken to be 0.06. The test will be performed as a one-sided test at $\alpha = 0.025$.

A 95% confidence interval for the difference $r_T - r_C$ will be computed using the Kaplan-Meier algorithm with the standard errors being computed using Greenwood's formula. The null hypothesis shall be rejected at $\alpha = 0.025$ if the upper confidence limit is less than 0.06.

Covariates will not be included in analysis of the primary endpoint.

11.5 Primary Endpoint (Superiority) and Secondary endpoints for labeling

The analysis for the superiority in the primary endpoint and secondary endpoints for labeling will be performed only if the primary endpoint passes the non-inferiority test.

The superiority in the primary endpoint and secondary endpoints will be evaluated for labeling purposes in the order shown below. Each endpoint will be tested between the treatment arms by a two-sided test at $\alpha = 0.05$. If any of the endpoints does not achieve statistical significance at $\alpha = 0.05$, the lower endpoints in the list will not be considered for this purpose. The analyses will be performed in the As Treated population.

1. New onset atrial fibrillation, as a superiority analysis comparing trial arms (Secondary endpoint for labeling)

Let r_T and r_C be the true new onset atrial fibrillation rate at 30 days for test and control arms respectively. The hypotheses for the superiority test are:

$$\begin{aligned} H_0: r_T &= r_C \\ H_A: r_T &\neq r_C \end{aligned}$$

The endpoint will be evaluated as a binary endpoint. The trial arms will be compared using the Fisher's exact test. The null hypothesis shall be rejected and the superiority will be established if the p-value of test is less than 0.05 and the point estimates $\hat{r}_T < \hat{r}_C$.

The counts and percentages of the new onset atrial fibrillation at 30 days will be presented for TAVR and SAVR arms, the p-value of trial arm comparison will

also be presented. The subjects with pre-procedural atrial fibrillation or those undergoing concomitant ablation will be excluded from the analysis unless CEC adjudicated the event as “new onset” or “both”.

2. Length of index hospitalization, as a superiority analysis comparing trial arms (Secondary endpoint for labeling)

Let d_T and d_C be the distribution of the true lengths of index hospitalization for test and control arms, respectively. For this analysis, patients who die before discharge will be considered to have been discharged on the death date. The hypotheses for the superiority test are:

$$\begin{aligned} H_0: d_T &= d_C \\ H_A: d_T &\neq d_C \end{aligned}$$

Length of index hospitalization will be treated as a continuous variable, with trial arms compared using the Wilcoxon rank-sum test. The null hypothesis shall be rejected and the superiority will be established if the p-value of test is less than 0.05 and the point estimates of the median lengths $\hat{d}_T < \hat{d}_C$.

The mean, standard deviation, median, minimum and maximum of Length of index hospitalization will be presented for TAVR and SAVR arms, the p-value of trial arm comparison will also be presented.

3. Primary endpoint as a superiority analysis comparing trial arms

The superiority test for the primary endpoint will be performed as a one-sided test at 0.025, where α is the amount of Type I error passed, The hypotheses for the superiority test are:

$$\begin{aligned} H_0: r_T &\geq r_C & \text{or equivalently} & & H_0: r_T - r_C &\geq 0 \\ H_A: r_T &< r_C & & & H_A: r_T - r_C &< 0 \end{aligned}$$

The following Z statistic will be used for the superiority test.

$$Z = \frac{\hat{r}_T - \hat{r}_C}{\sqrt{s_T^2 + s_C^2}}$$

The null hypothesis shall be rejected and the superiority will be established if the p-value of the one-sided Z test is less than 0.025.

4. KCCQ and death composite at the 30 day visit, as a superiority analysis comparing trial arms (Secondary endpoint for labeling)

Let r_T and r_C be the true rate of the composite events at 30 days for test and control arms respectively. The hypotheses for the superiority test are:

$$H_0: r_T = r_C$$

$$H_A: r_T \neq r_C$$

The endpoint will be evaluated as a binary endpoint. The trial arms will be compared using Fisher's exact test. The null hypothesis shall be rejected and the superiority will be established if the p-value of test is less than 0.05 and the point estimates $\hat{r}_T < \hat{r}_C$.

A patient will be counted as meeting this endpoint if one or more of the following three conditions hold.

- a) The patient dies on day 30 or earlier, whether or not a KCCQ score has been collected within the follow-up window.
- b) The KCCQ score at the 30 day visit is < 45 .
- c) The KCCQ score at 30 days is ≥ 10 points decreased from the baseline score.

Missing data will be handled as described in section 11.8.5.

5. Death/All Stroke composite at 30 days, as a superiority analysis comparing trial arms (Secondary endpoint for labeling)

Let r_T and r_C be the true rate of the death/all stroke composite events at 30 days for test and control arms, respectively. The hypotheses for the superiority test are:

$$H_0: r_T = r_C$$

$$H_A: r_T \neq r_C$$

The endpoint will be evaluated as a binary endpoint. The trial arms will be compared using the Fisher's exact test. The null hypothesis shall be rejected and the superiority will be established if the p-value of test is less than α and the point estimates $\hat{r}_T < \hat{r}_C$.

The counts and percentages of the composite event at 30 days will be presented for TAVR and SAVR arms, the p-value of trial arm comparison will also be presented.

6. All Stroke at 30 days, as a superiority analysis comparing trial arms (Secondary endpoint for labeling)

Let r_T and r_C be the true stroke rate at 30 day for test and control arms, respectively. The hypotheses for the superiority test are:

$$H_0: r_T = r_C$$

$$H_A: r_T \neq r_C$$

Stroke will be evaluated as a binary endpoint. The trial arms will be compared using the Fisher's exact test. The null hypothesis shall be rejected and the superiority will be established if the p-value of test is less than α and the point estimates $\hat{r}_T < \hat{r}_C$.

The number of events, number of patients with event and Kaplan-Meier estimates of stroke rate at 30 day will be presented for TAVR and SAVR arms, the p-value of trial arm comparison will also be presented.

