6.2 Secondary Endpoints for Labeling

1. New onset atrial fibrillation at 30 Days
2. Length of index hospitalization
3. Death, KCCQ < 45 or KCCQ decrease \geq 10 points at 30 days
4. Death/All Stroke composite at 30 days
5. All Stroke at 30 days

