9.5 AE Reporting Requirements

All relevant AEs will be captured from the time of randomization/enrollment until the study patient's participation has ended (i.e. completion of study or withdrawal of consent).

Adverse events must be followed until resolution, stabilization or study completion. The AE and/or SAE should be reported, and CRF Forms completed **as soon as possible but no later than 10 working days of awareness**.

In the event that the EDC system is not in service, a paper copy of the AE Case Report Form (CRF) must be faxed or emailed to Sponsor THV Medical Safety at [contact] or emailed to [contact] **within 10 business days of becoming aware of the event**. At the time of initial notification, the following minimal information must be provided:

- Study site
- Patient ID
- Adverse event description
- Causal relationship to device and implant procedure
- Aware date

The site will provide a copy of supporting documentation (example: admission H&P, implant procedure reports, anesthesia records, discharge summary, echocardiogram and ECG reports, laboratory results, etc.) for all endpoint-related and device or procedure-related events and UADEs to Edwards Lifesciences (or designee). Source documentation may be requested by the Edwards Medical Safety Officer for other AEs in order to verify that events are being assessed appropriately.

Enrolling sites must provide to the Sponsor at a minimum an admission history and physical, index procedure report and discharge from index hospitalization along with relevant echocardiographic reports. This will be done irrespective of subject having any AE/SAE.

All AEs must be reported over the 12 month period following the initial valve implant procedure. Reportable AEs after year 1 through year 10 or study exit include only the following events:

- All AEs that are assessed or suspected to be device or implant procedure related
- All AEs that meet the criteria for serious adverse event irrespective of device or implant procedure relationship
- All AEs considered to be an Unanticipated Adverse Device Effect

The site Principal Investigator is responsible for informing the Institutional Review Board (IRB) of SAEs, UADE and/or AEs as required. A copy of this report should be provided to the Sponsor (or designee).

Events that do not Require Reporting to the Sponsor:

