11.8.7 Adverse event analysis

- Adverse event analysis will involve both site and CEC reporting.
 - Where events have been adjudicated by the CEC, those adjudications will be used in preference to site reports.
 - Where site events are analyzed, the MedDRA coding will be used. The underlying site evaluations will not be used for analysis, but may appear in listings as appropriate.
- Adverse events to be analyzed include the composites involved in the primary and secondary endpoints, as well as all events contained in these composites. All events adjudicated by the CEC will also be analyzed.
- Adverse event tables will present data at 30 days, 6 months, and 1 year. The tables will include counts of events, patients with event, and Kaplan-Meier event rates at the specific time point. The trial arms will be compared by the log-rank test
- Late adverse events (> 30 days) will be analyzed by a constant hazard model, and upper one-sided confidence limits will be given for the rates.

- Adverse event data past 1 year will be presented as counts of events and patients with event. No formal analyses will be performed for such data.

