12.3 Clinical Event Adjudication Committee (CEC)

The Clinical Events Committee (CEC) will adjudicate endpoint events and provide assessment of SAEs and device/procedure relatedness from enrollment through the primary endpoint. The CEC will include cardiologists and cardiothoracic surgeons with experience in the field of aortic stenosis who are not involved in the study and have no conflict of interest. CEC activities will be defined in the CEC Charter.

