12.7 Data Management

Edwards Lifesciences will provide data management through a secure, password protected Electronic Data Capture (EDC) system accessible via the Internet. A unique Patient ID will be assigned for each patient enrolled in the study. All pertinent data will be entered by the study site and core lab personnel into the electronic Case Report Forms (eCRFs).

Every reasonable effort should be made to complete data entry within 5 business

days of data collection. Data review by Edwards Lifesciences personnel will occur remotely as well as during on site monitoring. Data discrepancies will be queried and resolved through the EDC system.

The site Principal Investigator or designee must ensure the accuracy and completeness of the recorded data and then provide his/her electronic signature on the appropriate eCRFs. Changes to data previously submitted to the Sponsor will require a new electronic signature to acknowledge/approve the changes.

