12.8 Monitoring Procedures

All clinical sites will be monitored periodically by Edwards Lifesciences or designee to ensure compliance with the protocol and the Investigator's Agreement and that all study patients have been properly consented. The monitor will ensure that the completed eCRFs match the source documents and work with the site to resolve differences through electronically generated queries or formal action items.

Edwards Lifesciences will evaluate circumstances where an investigator deviates from the clinical protocol and will retain the right to remove either the investigator or the investigational site from the study.

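### The 30-day new-onset AF analysis re-admits patients with prior AF or concomitant ablation only when they have a qualifying event, so the denominator depends on the outcome

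*Combined protocol and SAP*

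**What the plan says.** Section 6.2 lists "New onset atrial fibrillation at 30 Days" first among the secondary endpoints for labeling. Section 11.5 item 1 analyses it as a binary endpoint in the As Treated population. The test is Fisher's exact test, two-sided at 0.05, and superiority also requires a lower observed rate in the TAVR arm. Counts and percentages are to be presented by arm. The analysis set is defined by this rule: "The subjects with pre-procedural atrial fibrillation or those undergoing concomitant ablation will be excluded from the analysis unless CEC adjudicated the event as"; the two qualifying calls are *new onset* and *both*.

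Section 11.5 tests in a fixed order, once primary non-inferiority has passed. If an endpoint fails, "the lower endpoints in the list will not be considered for this purpose". AF is item 1 of six; superiority on the primary endpoint is item 3.

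Appendix B defines continuous AF, but neither new-onset AF nor the category *both*. Section 11.2 plans selected ITT sensitivity analyses and section 11.8.5 plans tipping-point analyses for the primary and KCCQ endpoints. None is described for this exclusion rule.

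**The concern.** The rule excludes a group and then takes back those members who had the event. A re-admitted patient adds one to the numerator and one to the denominator; an event-free patient of the same kind adds to neither. The resulting percentage is not a risk in any population that could be defined before the outcome was known.

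The natural reason for such a clause is to rescue patients whose AF history was recorded wrongly. But section 12.3 says the clinical events committee (CEC) "will adjudicate endpoint events and provide assessment of SAEs and device/procedure relatedness", so this route opens only when there is an event to adjudicate. A patient with the same recording error who stays free of AF has no such route. Routes that ignore the outcome already exist. Under section 9.5 the admission history goes to the sponsor for every patient ("This will be done irrespective of subject having any AE/SAE"). Section 12.7 says "Data discrepancies will be queried and resolved through the EDC system", and section 12.8 says "The monitor will ensure that the completed eCRFs match the source documents".

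A smaller point: ablation takes place at the procedure, after randomisation, so randomisation does not balance it. Excluding on it matters only for ablation patients without recorded AF.

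At stake are the reported AF rates and the first gate of the labeling sequence: if it fails, none of the five tests below it is considered.

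**Working it through.** **Inputs.** Section 11.1 gives a chosen size of 1000 and section 3.0 gives 1:1 allocation, hence 500 per arm. (Section 4.0 allows up to 1182 randomised.) The share with prior AF or ablation, the AF rate and the number re-admitted are not in the documents. Assumed here: 5–25% with prior AF, leaving N0 = 375 to 475 per arm (425 as the middle case), and k = 1 to 5 re-admitted per arm.

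**The plan's own figures.** No rate, sample size or power is stated for the AF endpoint, so there is nothing to reproduce. The one sample size that is stated, 864 for primary non-inferiority, does reproduce: (1.960 + 1.282)² × (0.166 × 0.834 + 0.146 × 0.854) / (0.06 + 0.02)² = 432 per arm.

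**Shift in the reported rate.** With e0 events among N0 patients without prior AF or ablation, r = e0/N0, and k re-admitted patients who are all events:

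- exclude all: e0/N0
- plan's rule: (e0 + k)/(N0 + k)
- difference: k(1 − r)/(N0 + k), positive whenever k > 0 and r < 1

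For example, N0 = 425, r = 0.30 and k = 5 give 5 × 0.70/430 = 0.81 points.

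| Setting | r = 5% | r = 10% | r = 30% | r = 40% |
|---|---|---|---|---|
| N0 = 425, k = 1 | – | – | +0.16 | +0.14 |
| N0 = 425, k = 5 | +1.10 | +1.05 | +0.81 | +0.70 |
| N0 = 375, k = 5 | +1.25 | +1.18 | +0.92 | +0.79 |
| N0 = 475, k = 5 | +0.99 | +0.94 | +0.73 | +0.62 |

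**Close results.** Two-sided Fisher p-values, TAVR v SAVR. The include-all column counts the same events over all 500 patients per arm.

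| Exclude all | Re-admitted | Plan's rule | Include all |
|---|---|---|---|
| 43/425 v 62/425: 0.060 | 1 SAVR | 43/425 v 63/426: 0.048 | 43/500 v 63/500: 0.0506 |
| 43/425 v 60/425: 0.092 | 3 SAVR | 43/425 v 63/428: 0.048 | 43/500 v 63/500: 0.0506 |
| 43/425 v 64/425: 0.038 | 2 TAVR | 45/427 v 64/425: 0.052 | 45/500 v 64/500: 0.067 |

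**False TAVR superiority with no true difference** (nominal 2.5% for this direction).

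- *Balanced arms:* 425 at risk plus 75 with prior AF per arm, and the same re-admission share (2% or 7%) in both arms, 20,000 trials per scenario. The rate is 2.3% at a 10% AF rate and 2.1% at 30%, against 1.9% with no re-admissions. The level holds.
- *Unequal excluded shares:* 500 per arm, 6,000 trials per scenario. With 15% TAVR v 20% SAVR, and AF and CEC-call rates both 20%, the rate is about 5%, against about 2% under exclude-all. With 15% v 25% and the same rates it is 10.9%, against about 2%. With 15% v 20% and both rates 10% it is 4.0%, against about 2%.

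**Large difference.** 21/425 v 149/425 gives p = 3 × 10⁻³⁰; with five re-admitted per arm it is 1.5 × 10⁻²⁸.

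**The case against.** The strongest counter-argument is that the close examples mostly show the effect of counting an extra event, not of the denominator. In the first example, adding the SAVR event with the denominator held at 425 also gives p = 0.048. Whether such events should count is a choice of estimand, and exclude-all is only one option. This is partly right: most of the movement does come from the event, and in the third example include-all is also non-significant. But in the first two examples the plan's rule is significant while both outcome-independent sets are not. An estimand that counts these events must also count the event-free patients of the same kind.

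Second, demonstrated harm is limited. Balanced re-admissions of one to five per arm leave the 43 v 62 comparison non-significant (0.062 to 0.071) and 43 v 64 significant (0.040 to 0.046). A wider gap, 43 v 75, survives five TAVR-only re-admissions (p = 0.008). Randomisation should roughly balance prior AF, and the documents give no ablation frequency by arm. All of this stands and limits the severity.

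Third, *new onset* and *both* may be explained in the CEC Charter, which is not in the documents, and a *new onset* call may be the CEC overruling a site label, in line with section 11.8.7: "Where events have been adjudicated by the CEC, those adjudications will be used in preference to site reports". That may explain the intent. It does not give an event-free patient the same correction.

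**Conclusion.** The concern holds. As written, the rule selects patients on the outcome, and nothing else in the documents repairs it. The reported AF rate exceeds the exclude-all rate in any arm with a re-admitted patient: by about 0.1 to 0.8 points for one to five re-admissions at a 30–40% AF rate with 425 at risk, and by about 1.1 points for five at 5–10%.

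The direction of bias in the arm difference cannot be known from the documents. The test keeps its level if excluded shares and CEC calls match across arms, and may not if they differ. A large treatment difference would survive; a close one might not. This should be fixed because the endpoint supports a label claim and gates five further tests. Confidence is high in the reading of the rule. Every size above rests on assumed AF rates, shares and re-admission counts.

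**What to change.** In section 11.5 item 1:

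1. Within the As Treated population, define the analysis set by pre-procedural AF status from medical history and the screening ECG. Allow corrections only through the ordinary query and source-check process, without regard to outcome.
2. Delete the exception for CEC-adjudicated events.
3. Report CEC *new onset* or *both* events in excluded patients on a separate line, and define both terms.
4. Add a sensitivity analysis that keeps the whole prior-AF/ablation group in the denominator and counts their adjudicated events.
5. Apply any ablation rule to all patients regardless of outcome. Preferably do not use ablation to define the set, since it follows randomisation.

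The cost is one rule, one analysis flag and one sensitivity table. Section 8.1 already collects medical history and a 12-lead ECG at screening.

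There are downsides. Some adjudicated events leave the tested endpoint, which needs a stated exception to the section 11.8.7 preference for CEC adjudications. Reported AF rates may be slightly lower. Section 8.3 schedules no Day 0 ECG, so identifying AF that arises between screening and the procedure would rely on the admission history and on adverse events, which section 9.5 captures from randomisation.
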